## 7.2.6.7 Early Termination (ET) Visit Mapping

For safety data from ET visits, the data will not be mapped. For subjects in Cohort 1, ET visits will be combined with Week 26 visits, and the time point labelled "Week 26/ET." For subjects in Cohort 2, ET visits will be combined with Week 52 visits, and the time point labelled "Week 52/ET."

For efficacy data from ET visits, the data will be mapped using the analysis visit window and the data handling rules as defined in Section 7.2.2 and 7.2.3. These mapped analysis visit data will be used for analyses and summaries.

## 7.3 Statistical Analyses

## 7.3.1 Disposition

Subject disposition will be summarized by treatment group and overall, as appropriate. The disposition summary will include:

- Number of subjects screened;
- Number and percent of subjects who failed screening and screen failure reasons;
- Number of subjects included in the SAS;
- Number of subjects included in the FAS;
- Number and percent of subjects in Cohort 1 and in Cohort 2 who completed as per protocol for both the FAS and the SAS;
- Number and percent of subjects in Cohort 1 and Cohort 2 who withdrew prior to completing the study, and associated primary reason for withdrawal, for both the FAS and the SAS.

#### 7.3.2 Protocol Deviations

All protocol deviations will be listed, sorted by Cohort, then treatment group, investigative site and subject number, and date of protocol deviation.

## 7.3.3 Study Drug Administration

The length of time that the VC-01 units were implanted will be summarized by Cohort, treatment group and overall, using the SAS. The summarization will include:

- Overall duration of exposure in days (calculated as [Date of explanation of last unit of any type] [Date of implantation of first unit] + 1);
- Number of VC-01-DF units implanted;
- Duration of exposure in days of VC-01-DF units (calculated as [Date of explanation of last VC-01-DF unit] [Date of implantation of first VC-01-DF unit] + 1);
- Number of sentinel units implanted;
- Duration of exposure in days of sentinel units (calculated as [Date of explanation of last sentinel unit] [Date of implantation of first sentinel unit] + 1);
- Number of subjects with total planned number of units implanted and, if total not implanted, reason all units not implanted;
- Investigator's overall assessment of the implant surgical procedure;

- Number and percentage of subjects with a premature VC-01-DF unit explanted, and reason for premature explantation; and
- Number and percentage of subjects with a premature VC-01-DF unit explanted who remained in the study.

## 7.3.4 Demographics/Baseline Characteristics and Medical History

Demographic information and subject characteristics such as gender, race, age, and baseline vital signs will be summarized by treatment group for Cohort 1 and Cohort 2 using the FAS.

Pertinent medical history will also be summarized similarly using the SAS. For medical history, all medical conditions and surgical procedures will be classified by system organ class (SOC) and preferred term (PT) using the Medical Dictionary for Regulatory Activities (MedDRA). The number and percent of subjects with each medical condition and surgical procedure will be provided for each SOC and PT, by cohort and treatment group.

#### 7.3.5 Prior and Concomitant Medications and Procedures

Concomitant medications will be categorized into medications given as part of surgical procedures and medications not given as part of surgical procedures. Diabetic medications will not be included.

Summarizations of prior and concomitant medications and procedures will be provided by Cohort and treatment group. The concomitant medications and procedures summary will be broken out separately for surgical and non-surgical medications (procedures will be considered non-surgical).

All medications will be coded using World Health Organization (WHO) drug classifications. The number and percent of safety subjects will be tabulated by Anatomical, Therapeutic, and Chemical (ATC) class and by preferred name.

# 7.3.6 Primary Analysis

## Cohort 1 Primary Analysis

*The FAS will be used for the histology summarizations, which include:* 

- The percentage of viable graft cells at post-implant time points relative to preclinical models. The Sponsor initially plans to explant the majority of sentinel units at the Visit 6/Week 4 and Visit 8/Week 12 time points. However, as data are collected in the trial, it may inform that evaluation at additional time points is required.
- The percentage of graft cells staining positive for markers of beta cells at post-implant time points relative to pre-clinical models. The Sponsor will select appropriate biomarker staining to identify and quantify the amount of beta cells (e.g., insulin +, CHGA+, NKX6-1+).

Histology results will be summarized by explant time point, anatomical location, and treatment group for Cohort 1.

## Cohort 2 Primary Analysis

For Cohort 2 subjects, the FAS will be used to analyze the primary efficacy endpoint, the change from baseline to Week 26 in C-peptide  $AUC_{0-4h}$  following an MMTT. The endpoint will be analyzed using analysis of covariance (ANCOVA), with treatment group as a factor and baseline C-peptide  $AUC_{0-4h}$  as a covariate. The output from the ANCOVA will include the least squares mean (LSM) and standard error (SE) for each treatment group.

## 7.3.7 Secondary Analyses

## 7.3.7.1 Cohort 1 Secondary Analyses

For Cohort 1 subjects, the FAS will be used to perform the qualitative assessment of the severity of the host immune response as rated at post-implant time points. These results will be summarized by explant time point, anatomical location, and treatment group. For the incidence of immune sensitization, any subject experiencing a confirmed sensitization will have an AE of 'sensitization' in the clinical study database. A listing will be provided for all subjects with a suspected event (the presence of donor anti-HLA antibodies absent prior to implant), with a column in the listing that indicates whether it is a confirmed immune sensitization (either confirmatory histological observations from at least one explanted unit and/or the presence of clinical symptoms; will have a corresponding 'sensitization' AE).

The number of Cohort 1 subjects experiencing off-target growth as evidenced by implanted VC-01 units via lumen ultrasound measurements (lumen thickness > 1 mm) or by histological examination of explants will be summarized by treatment group.

Unless otherwise specified, the SAS will be used for the safety summarizations for the Cohort 1 subjects. Adverse events and SAEs will be summarized by system organ class (SOC), by severity, and by relationship. This will be done by treatment group and overall. The summarization of AEs will focus on only those events that are TEAEs, but the AE listings will include all reported AEs regardless of when they started.

For TEAEs, an overall summary will include the number and percentage of subjects experiencing:

- a TEAE;
- a TEAE by toxicity grade;
- a TEAE by relationship to VC-01 combination product;
- a TEAE by relationship to the surgical procedures required for VC-01 administration;
- a TEAE leading to study withdrawal;
- a treatment emergent SAE (TESAE);
- a TESAE by toxicity grade;

- a TESAE by relationship to VC-01 combination product;
- a TESAE by relationship to the surgical procedures required for VC-01 administration.

This overall summary table will include the number and percentage of subjects and also the total number of TEAE episodes. If a subject has repeated episodes of a particular TEAE, all episodes will be counted in the summary table's total number of episodes.

Other AE tables that will be produced will include:

- A summary of subjects experiencing a TEAE by SOC and PT;
- A summary of subjects experiencing a TEAE by SOC, PT and toxicity grade;
- A summary of subjects experiencing a TEAE related to investigational product by SOC, PT;
- A summary of subjects experiencing a TEAE related to the surgical procedures required for VC-01 administration by SOC, PT;
- A summary of subjects experiencing a TESAE by SOC and PT;
- A summary of subjects experiencing a TESAE by SOC, PT and toxicity grade;
- A summary of subjects experiencing a TESAE related to investigational product by SOC, PT;
- A summary of subjects experiencing a TESAE related to the surgical procedures required for VC-01 administration by SOC, PT; and
- A summary of subjects experiencing a TEAE leading to study withdrawal by SOC and PT.

A listing of adverse events of special interest (AESIs) will also be provided.

Other safety data, such as vital signs and clinical laboratory data will be summarized by study visit and treatment group for the Cohort 1 subjects. Change from baseline in safety data will also be summarized in a similar manner.

The number of Cohort 1 subjects undergoing a premature VC-01 unit explant will be provided in a listing (separate from the overall explant listing) which includes the reason for explantation (i.e., safety issue, malfunction, damaged, planned explant, etc).

For the secondary safety endpoint of immune response as measured by serum immunoglobulin and hematological assays, any Cohort 1 subject who appears to be having an immune response will have all relevant data described in a clinical narrative. In addition, data of interest from the assays may be summarized by treatment group and overall.

Physical examination data will be listed by subject. *Finally, implantation site* assessments will be summarized at each time-point post-implantation and each visit thereafter. For each site assessment symptom, the number of Cohort 1 subjects with the symptom at that time-point will be summarized by treatment group and overall.

## 7.3.7.2 Cohort 2 Secondary Safety Analyses

Unless otherwise specified, the SAS will be used for the safety summarizations for the Cohort 2 subjects. Adverse events and SAEs will be summarized by system organ class (SOC), by severity, and by relationship. This will be done by treatment group and overall. As with the Cohort 1 subjects, the summarization of AEs for Cohort 2 will focus on only those events that are TEAEs, but the AE listings will include all reported AEs regardless of when they started.

Other safety data, such as vital signs, clinical laboratory data, and hypoglycemic events will be summarized by study visit and treatment group, for the Cohort 2 subjects. Change from baseline in safety data will also be summarized in a similar manner. Physical examination data will be listed by subject.

The number of Cohort 2 subjects experiencing off-target growth as evidenced by implanted VC-01 units via lumen ultrasound (lumen thickness > 1 mm) measurements, or by histological examination of explants will be summarized by treatment group.

For immune response as measured by serum immunoglobulin and hematological assays, any Cohort 2 subject who appears to be having an immune response will have all relevant data described in a clinical narrative. In addition, data of interest from the assays may be summarized by treatment group and overall. For the incidence of immune sensitization, a listing will be provided for all subjects with a suspected event (the presence of donor anti-HLA antibodies absent prior to implant), with a column in the listing that indicates whether it is a confirmed immune sensitization (either confirmatory histological observations from at least one explanted unit and/or the presence of clinical symptoms; will have a corresponding 'sensitization' AE).

Implantation site assessments will be summarized at each time-point post-implantation and each visit thereafter. For each site assessment symptom, the number of Cohort 2 subjects with the symptom at that time-point will be summarized by treatment group and overall.

Finally, the number of Cohort 2 subjects undergoing a premature VC-01 unit explant will be provided in a listing (separate from the overall explant listing), which includes the reason for explantation (i.e., safety issue, malfunction, damaged, planned explant, etc.).

## 7.3.7.3 Cohort 2 Secondary Efficacy Analyses

Each of the secondary efficacy endpoints will be analyzed using an  $\alpha = 0.05$  level of significance. Given the large number of secondary efficacy endpoints, the p-values for these endpoints will be considered descriptive.

The FAS will be used to analyze the secondary efficacy endpoints, with the analysis for each endpoint performed within Cohort 2 subjects only. Change from baseline to Weeks 16, 20, 26 and 39 in C-peptide AUC0-2h following an MMTT and change from baseline to Week 52 in C-peptide AUC0-4h following an MMTT; change from baseline to Weeks 16, 20, 26, 39 and 52 in average daily insulin dose in the seven days preceding the clinic visit; and change from baseline to Weeks 16, 20, 26, 39 and 52 in time in euglycemic range, time in hypoglycemic range, and time in hyperglycemic range will each be analyzed using ANCOVA, with treatment group as a factor and the relevant baseline as a covariate.

Time to onset of biological response of C-peptide following an MMTT will be assessed using Kaplan-Meier curves, with the p-value from the logrank test also provided.

The percent of subjects who achieve a positive stimulated C-peptide (defined as > 0.2 ng/mL) after implant; the percent of subjects who achieve a 50% reduction in average weekly exogenous insulin dose from baseline to Weeks 16, 20, 26, 39 and 52; and the percent of subjects who achieve exogenous insulin independence, percent of subjects (of those achieving insulin independence) achieving  $HbA1c \le 7.0\%$  will each be analyzed using Fisher's exact test. The number and percent of subjects in each treatment group and the p-value from the Fisher's test will be provided (at each timepoint, where appropriate).

The percent of time spent with blood glucose values at various cut points as measured by each subject's CGM will be summarized descriptively. The percentages and change from baseline percentages will be summarized for each cut point (<54 mg/dL,  $\ge54$  to <70 mg/dL,  $\ge70$  mg/dL to  $\le180$  mg/dL, >180 mg/dL and >250 mg/dL) and for each treatment group.

Change from baseline in frequency of hypoglycemic events (24-hour; daytime [start between 6 a.m. – 12 a.m.]; nocturnal [start between 12 a.m. – 6 a.m.]) at Weeks 16, 20, 26, 39, and 52 will each be analyzed using ANCOVA, with treatment group as a factor and the relevant baseline as a covariate. This analysis will be performed separately using HEs from the patient-reported diary and from CGM.

The number and percent of subjects free of severe hypoglycemic events between study visits (Weeks 16-20, Weeks 20-26, Weeks 26-39, Weeks 39-52, and Weeks 16-52) will each be analyzed using Fisher's exact test. The number and percent of subjects in each treatment group and the p-value from the Fisher's test will be provided (at each time point, where appropriate). These analyses will be performed separately using HEs from patient-reported diary and HEs from CGM.

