13.6. Reasons for Withdrawal

Investigators will make reasonable efforts to keep enrolled subjects in the study. However, if a subject is prematurely removed from treatment, a termination visit must be performed. This would generally include all procedures outlined in Visit 11 (Week 26) for Cohort 1 and Visit 13 (Week 52) for Cohort 2 as well as the procedures outlined in follow-up Visit 12 (Week 27) for Cohort 1 and Visit 14 (Week 53) for Cohort 2. Adverse events should be followed until their resolution.

Subjects may withdraw from the trial at any time at their own request, or they may be withdrawn at any time at the discretion of the Investigator or Sponsor for safety or behavioral reasons.

There are subject-specific criteria and product-related criterion that will necessitate withdrawal from the study.

Cohorts 1 and 2

- Subject has a new onset, off-target cell growth within the unit confirmed by a board-certified pathologist as a teratoma and is considered related to VC-01.
- Subject appears to mount an immune or inflammatory response that puts the subject at risk for severe or serious immune reaction AEs. In this case, the Sponsor will assess the case fully (e.g., clinically and immune test results) and advise whether an explant of any units is advisable to facilitate continued participation.
- Subject becomes pregnant or in the Investigator's opinion is non-compliant with contraception requirements (Section 5.4.4).
- Implanted units appear to be damaged or malfunctioning (e.g., localized infections, damaged unit) resulting in severe or serious AEs. Note: In the case of a suspected

malfunctioning or damaged unit, the Sponsor will assess the case fully and advise whether an explant of any units is advisable. Explant of one unit may occur in this situation without requiring the withdrawal of the subject from the study upon request from the Sponsor.

Cohort 2 Only

• After a minimum of eight weeks post-implantation, the subject experiences three or more Severe Hypoglycemic Events (SHE) over a six-month period unrelated to anything other than VC-01. This assumes the SHE occurred despite reasonable adjustments in the exogenous insulin requirements and appropriate dietary adjustments.

If a subject meets any of these criteria, any remaining units will be explanted. The subject will be asked to follow-up with the study site post-explant in the long-term follow-up study.

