## **Efficacy**

- Change from baseline to Weeks 8, 12, 16, 20, and 39 in C-peptide  $AUC_{0-2h}$  and change from baseline to Week 52 in C-peptide  $AUC_{0-4h}$  following an MMTT.
- Change from baseline to Weeks 16, 20, 26, 39 and 52 in average daily insulin dose.
- Time to onset of biological response of C-peptide following MMTT.
- Percent of subjects achieving a positive stimulated C-peptide (defined as > 0.2 ng/mL) after implant
- Percent of subjects who achieve a 50% reduction in average weekly exogenous insulin dose from baseline to Weeks 16, 20, 26, 39, and 52.
- Percent of subjects who achieve exogenous insulin independence; of those subjects achieving insulin independence, the percent achieving HbA1c < 7.0%.

- Percent of time spent with blood glucose values at various cut points (e.g., <54 mg/dL, ≥54 to < 70 mg/dL, ≥70 mg/dL to ≤180 mg/dL, >180 mg/dL and >250 mg/dL) as measured by each subject's CGM.
- Change from baseline to Weeks 16, 20, 26, 39 and 52 in time-in-euglycemic range (≥70 mg/dL to ≤180 mg/dL), time-in-hypoglycemic ranges (<54 mg/dL and ≥54 to <70 mg/dL), and time-in-hyperglycemic ranges (>180 mg/dL and >250 mg/dL) as measured by each subject's CGM.
- Change from baseline to Weeks 16, 20, 26, 39, and 52 in weekly frequency of hypoglycemic events;
- Change from baseline in frequency of hypoglycemic events (24-hour; daytime [start between 6a.m.-12a.m.]; nocturnal [start between 12a.m.-6a.m.]) to Weeks 16, 20, 26, 39 and 52.
- Percent of subjects free of severe hypoglycemic events between study visits starting with Week 16 (i.e., Weeks 16-20, Weeks 20-26, Weeks 26-39, Weeks 39-52/ET, and Weeks 16-52/ET).

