## 7.2.6.3.1 Daily and Weekly Exogenous Insulin Dose

For subjects in Cohort 2, baseline average daily and average weekly exogenous insulin dose requirements will be calculated using up to 28 days of data. Baseline average daily and average weekly insulin requirements will be calculated using data starting at Day -1 (the day prior to implant) and working backwards for up to 28 days (through Day -28). For instances in which the available pre-implant data provides less than 28 days of data, post-implant data will be used to supplement, using Day 4 forward until 28 days of data are available. Data from days on which an MMTT or SOGCT was performed, will not be included in the calculation.

At Weeks 16, 20, 26, 39 and 52, the last 7 daily total exogenous insulin doses recorded in the log will be used to calculate the average daily and weekly exogenous insulin dose at that visit. The last 7 daily records must be within the previous 14 calendar days and may not include a day in which an MMTT or SOGCT was performed. There must be at least 4 different days worth of data for a particular timepoint to be considered evaluable.

The weekly average value will be calculated as:

7 \* (sum of the insulin doses during the period / number of days with insulin doses in the period).

The percent reduction in average weekly exogenous insulin dose from baseline at these visits will be calculated as:

(Average weekly insulin dose at post-baseline visit - baseline average weekly insulin dose)\*100/ baseline average weekly insulin dose.

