## 7.2.6.5 Frequency of HEs using Subject-Reported Diary Data

HE data collected from the subject-completed diaries will be used for assessment of efficacy. Investigators will review the HE logs in the diary at each study visit. Blank values in the HE log are considered to be 0 values.

HEs will be classified in six ways: total HEs, severe HEs (SHEs), nocturnal HEs, severe nocturnal HEs, daytime HEs, and severe daytime HEs. Total HEs are HEs that occur at any time during the 24-hour period; SHEs are HEs requiring the aid of another person to administer carbohydrates, glucagon, or other resuscitative assistance any time during the 24-hour period. Nocturnal HEs are HEs that start during the 12 a.m. -6 a.m. period; severe nocturnal HEs are SHEs that start during the 12 a.m. -6 a.m. period. Daytime HEs are HEs that start during the 6 a.m. -12 a.m. period; severe daytime HEs are SHEs that start during the 6 a.m. -12 a.m. period.

The baseline average weekly frequency of subject-reported HEs, SHEs, nocturnal HEs, severe nocturnal HEs, daytime HEs and severe daytime HEs will be calculated using up to 28 days of data. The baseline average weekly frequency will be calculated using data starting at Day -1 (i.e., the day prior to implantation) and working backwards for up to 28 days (through Day -28). For instances in which the available pre-implant data provides less than 28 days of data, post-implant data will be used from Day 4 forward until 28 days of data are available. Data from days on which the Screening SOGCT or the MMTT was performed will not be used in the calculation.

The total number of HEs, SHEs, nocturnal HEs, severe nocturnal HEs, daytime HEs, and severe daytime HEs occurring in the 14 days prior to each specified time point (Weeks 16, 20, 26, 39, and 52) will be used to calculate the weekly frequency of total HEs, SHEs, nocturnal HEs, severe nocturnal HEs, daytime HEs, and severe daytime HEs, respectively, at the specified time point. Data for HEs/SHEs should not be used if an MMTT was performed on that day.

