## 7.2.6.6 Frequency of HEs using CGM Data

CGM will be utilized, based on the below specified rules, to evaluate the number of hypoglycemic episodes (number of times blood glucose falls below 70 mg/dL) and the number of severe hypoglycemic events (number of times blood glucose falls below 54 mg/dL) for each subject:

- A set of CGM readings < 70 mg/dL or <54 mg/dL, with a minimum overall duration of 15 minutes
- Up to two consecutive readings >= 70 mg/dL (or >= 54 mg/dL for separate summary) are allowed within the same episode
- If a subsequent episode starts within 60 minutes of the start of the previous episode, then they are combined and counted only as one episode

The total number (over the entire 24-hour time period) of episodes will be calculated as well as the number of nocturnal (starts during the 12 a.m. - 6 a.m. period) episodes and the number of daytime (starts during the 6 a.m. to 12 a.m.) episodes.

Baseline CGM-reported HE data will be calculated using up to 28 days of data. Baseline CGM-reported HEs will be recorded starting at Day -1 (i.e., the day prior to implant) and working backwards for up to 28 days (through Day -28). For instances in which the available pre-implant data provides less than 28 days of data, post-implant data will be used from Day 4 forward until 28 days of data are available. These data will be used to calculate the baseline number of weekly total episodes, weekly nocturnal episodes, and weekly daytime episodes. In addition, the CGM data from the 14 days prior to each scheduled clinic visit will be used to calculate the number of weekly total episodes, the number of weekly nocturnal episodes, and the number of weekly daytime episodes for each of these visits. For baseline and on-study time points, data from days on which an SOGCT (baseline only) or MMTT was performed should not be used.

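### The percentage of Cohort 2 subjects free of severe hypoglycemia takes no account of incomplete observation, so in expectation it overstates freedom from these events

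*SAP*

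**What the plan says.** SAP 4.2 (Efficacy) lists as a secondary endpoint the percentage of subjects free of SHEs between visits from Week 16. The later intervals are "Weeks 26-39, Weeks 39-52/ET, and Weeks 16-52/ET". SAP 7.3.7.3 analyses "The number and percent of subjects free of severe hypoglycemic events between study visits" by Fisher's exact test in Cohort 2 FAS subjects. There the last and overall intervals are written as Weeks 39-52 and 16-52, without the early-termination suffix. Two data sources are used: "These analyses will be performed separately using HEs from patient-reported diary and HEs from CGM".

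For the diary, SAP 7.2.6.5 states: "Blank values in the HE log are considered to be 0 values". For CGM, SAP 7.2.6.6 builds an episode from actual low readings lasting at least 15 minutes overall and gives no minimum wear. It takes weekly frequencies from a fixed look-back: "the CGM data from the 14 days prior to each scheduled clinic visit will be used to calculate the number of weekly total episodes".

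Other endpoints have safeguards that this one lacks:
- SAP 7.2.6.3 says blank insulin entries are not zeros, and 7.2.6.3.1 adds: "There must be at least 4 different days worth of data for a particular timepoint to be considered evaluable".
- SAP 7.2.6.2 censors time to C-peptide response at study exit.
- SAP 7.2.5 leaves subjects with missing values out of change-from-baseline analyses.

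Protocol 13.6 classes a subject whose final explant the Sponsor brings forward for non-safety reasons as a completer, not an early termination.

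**The concern.** A yes/no status of having had no event depends on how long one looks. Under the endpoint definition, an event-free subject who stops early is scored on the time seen but is counted alongside subjects followed for the full 36 weeks. The blank-equals-zero rule does the same within follow-up: a day on which the diary was not opened reads as a day without an event. Sponsor-expedited explants add short follow-up that a table of early terminations would not reveal.

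At stake is how the percentages are read. They would appear in the study report as evidence on hypoglycemia under the implant, and they improve as observation declines. A comparison between dose groups is distorted as well if follow-up or sensor wear differs between them.

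**Working it through.** **Inputs from the documents.** SAP 7.2.2 sets Week 16 at Day 113 and Week 52 at Day 365. The span is 365 - 113 = 252 days = 36 weeks, or T = 252/365.25 = 0.690 years. The documents give no expected SHE-free percentage, SHE rate or dropout rate, so there is no planned figure to reproduce.

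**Assumptions.** A constant SHE rate r of 0.5, 1 or 2 per year; a fraction d leaving early, independently of SHE risk; every event-free leaver counted as free, as the SAP 4.2 intervals imply.

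**Step 1, exits spread evenly over the interval.**
True = exp(-rT).
Reported = (1 - d) exp(-rT) + d [1 - exp(-rT)]/(rT).
For r = 1 and d = 0.3: 0.7 × 0.5016 + 0.3 × (0.4984/0.690) = 0.351 + 0.217 = 0.568.

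| SHE rate per year | True | 10% leave | 30% leave | 50% leave | Excess at 30% |
|---|---|---|---|---|---|
| 0.5 | 70.8% | 72.2% | 74.9% | 77.7% | 4.1 points |
| 1 | 50.2% | 52.4% | 56.8% | 61.2% | 6.6 points |
| 2 | 25.2% | 28.1% | 33.9% | 39.7% | 8.7 points |

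**Step 2, all leavers exit at Week 20, after 4 of 36 weeks.** This is close to the worst case.
Reported = 0.7 exp(-36r/52) + 0.3 exp(-4r/52).
- r = 0.5: 78.4% against 70.7%, excess 7.7 points.
- r = 1: 62.8% against 50.0%, excess 12.8 points.
- r = 2: 43.3% against 25.0%, excess 18.3 points.

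The true values differ slightly from step 1 because this step uses a 52-week year.

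**Step 3, does censoring repair it?** A simulated Kaplan-Meier estimate (n = 200,000, 30% leaving evenly) gave 70.8%, 50.0% and 25.0%, within 0.2 points of the true 70.8%, 50.2% and 25.2%.

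**Step 4, would dropping incompletely observed subjects repair it?** Not if only the event-free leavers are dropped. In the Week 20 scenario at r = 1, the percentage becomes 0.7 × 0.5004 / [0.7 + 0.3 × (1 - 0.9260)] = 0.3503/0.7222 = 48.5%, against 50.0%. The bias then runs downward.

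**Step 5, CGM, by inference.** An episode needs readings, so a gap can hide one but cannot create an event in a subject who had none. If only a fraction w of time is observed, at random, and gaps pass as event-free, the expected percentage is exp(-rTw). At one CGM event per year it is 50.2%, 61.7% and 70.8% for w = 100%, 70% and 50%.

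**Step 6, group comparison.** Two groups of 20 with the same true rate of 2 per year were simulated 20,000 times. With 10% leaving in both, the percentages are 28% and 28%, and Fisher's test rejects at 0.05 in 2.5% of runs. With 10% against 40% they are 28% and 37% (5.1%). With 0% against 60% they are 25% and 43% (13.6%).

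**The case against.** The best counter-argument is that the text is less settled than steps 1 and 2 assume. SAP 7.3.7.3 drops the early-termination suffix, and SAP 7.2.6.7 maps efficacy data from early termination visits to the matching visit window. Whether a subject who left at Week 20 stays in the Weeks 16-52 denominator is therefore never said outright. Part of this stands: the sections need reconciling. But the endpoint definition does carry the suffix, the analysis set is the FAS, and no rule removes or censors such a subject.

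Two stronger readings are tempting and not supported:
- **A subject who never wore the sensor is scored as free.** The SAP does not say this. Its zero rule covers the diary only, and how absent CGM data enter the SHE-free count is unstated. The 14-day look-back belongs to weekly frequency, a different endpoint.
- **The withdrawal rule improves later intervals by selection.** Protocol 13.6 removes a subject if "the subject experiences three or more Severe Hypoglycemic Events (SHE) over a six-month period", but only for events attributable to nothing but VC-01 despite insulin and dietary adjustment. A subject with such an event after Week 16 already counts as not free for Weeks 16-52. Nothing shows that the selection would be material.

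Safeguards also exist. Protocol 7.16 has subjects contact the site about SHEs between visits, and the Investigator reviews entries at each visit and records events on a CRF. This limits missed SHEs during follow-up. It does nothing for time after exit, and SAP 7.2.6.5 still bases the efficacy assessment on the diary. Disposition and exposure tables let a reader see that follow-up was short, but do not correct the percentage.

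**Conclusion.** The point holds for the diary-based percentage. As written, incomplete observation can only raise it in expectation. With 30% leaving early, the overstatement for Weeks 16-52 is about 4 to 9 points with even exits and 8 to 18 points with all exits at Week 20, over 0.5 to 2 SHEs per year. These sizes rest wholly on assumed rates and exit patterns. With a rate near zero or near-complete follow-up the bias disappears.

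For CGM the direction is an inference from the episode definition and the missing wear rule. Comparisons between dose groups are distorted only if follow-up or wear differs by group. A reader might conclude that the trial's inference is compromised. The documents do not support that: no hypotheses are tested and the secondary p-values are declared descriptive. The damage is to the descriptive percentages themselves, which is reason enough to amend the SAP.

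**What to change.** 1. Make a Kaplan-Meier estimate of SHE-free status from Week 16 the main summary, censored at the last observed diary day or final explant, whichever comes first. Add SHEs per observed patient-year with a 95% confidence interval.
2. Reconcile SAP 4.2 and 7.3.7.3 on the early-termination suffix, and state who is in each interval's denominator. Show the number at risk and the observed time beside each interval percentage. Always keep subjects with an SHE as events, and do not drop only the event-free leavers (step 4).
3. Replace the blank-equals-zero rule in SAP 7.2.6.5. A blank hypoglycemia log can remain a zero on a day with other diary entries, but a day with no diary completion at all should be unobserved time.
4. Express CGM episodes per 7 × 24 hours of actual wear, with a minimum wear fixed in advance, and apply that minimum to the CGM SHE-free count too.

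The cost is SAP wording and modest programming. Explant dates, daily diary entries and CGM readings are already collected. The percentage will be less favourable and less precise. The Kaplan-Meier estimate assumes that leaving is unrelated to SHE risk, so reasons for exit should be tabulated beside it.
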